3.4 Study Duration

The anticipated duration of the clinical trial is approximately 4 years from the first patient enrolled to the last patient complete.

Individual patients will participate in the study for up to 35 days with a study treatment period of up to 120 hours of study CRRT post-randomization. At the conclusion of study treatment, patient adverse events and serious adverse events will be collected for a period of 30-days.

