6.10 Adverse Events Assessments

An AE is any untoward medical occurrence in a patient or clinical investigational patient administered a study product, and that does not necessarily have a causal relationship with the treatment or drug. An AE can therefore be any unfavorable and unintended sign (including an abnormal laboratory function), symptom (eg, rash, pain, discomfort, fever, dizziness, etc.), organ dysfunction (eg, cardiovascular failure, pancreatitis, etc.), systemic illness (eg, sepsis), or outcome of death temporally associated with the use of the study product, whether or not the event is considered associated with the study product.

- Laboratory and vital sign abnormalities qualify as AEs if medical intervention is required to treat or address the abnormality, if the patient must be discontinued from the study due to the abnormality, or if the value exceeds specific limits defined by the standard-of-care as qualifying it as an AE.
- An elective procedure/surgery that occurs during the course of a study, but is being performed for a documented pre-existing condition and was pre-planned prior to study entry will not qualify as an AE. If, however, the pre-existing condition unexpectedly deteriorates during the study requiring the procedure/surgery to be performed earlier than planned, the condition for which the procedure/surgery is being performed will qualify as an AE.

Adverse events will be collected starting from the time the patient signs the ICF until 30-days post study treatment period (end of the study). During the course of the study, the Investigator or designee shall monitor each patient for the occurrence of any AE. If an AE occurs, a full description of the event should be recorded including the date of onset, severity, time course, description, actions taken, and causal relationship of the AE to the study product(s). Investigators should review and reference the Causality definitions located in Section 6.10.1 when determining the relationship of the AE to the study product. The investigators may also discuss the event(s) with the Baxter Medical Monitor, but the Investigator must make, document and report the relationship for every AE. All AEs must be documented in source documents and on the eCRFs, no matter how common they are for a particular patient and regardless of the causality assigned by the Investigator.

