7. STUDY ACTIVITIES

7.1 Training on the Administration of Prismocitrate 18

The clinical sites will be required to be current users of Prismaflex Device Platform and users of citrate as an anticoagulant for CRRT circuits. The end users at these sites are authorized to use of the CRRT machines and regional citrate anticoagulation at their

institutions. Additional training on the administration of Prismocitrate 18 will be provided by the Sponsor. At the completion of training the site investigator and other end users (as delegated by an investigator) will complete an Evaluation (refer to 1407-004 Protocol Training Assessment 2015May26). Additional assessment materials for specific end user groups may be provided as needed or as determined by an investigator.

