7.5 End of Treatment or Early Termination Procedures

The following End of Treatment information will be collected and procedures or evaluations will be performed after completion of study CRRT during the Treatment Period (up to 120 hours of study CRRT):

- Physical exam including weight.
- Vital signs.
- Adverse events/serious adverse events (if not previously reported).
- Concomitant medications.
- Clinical laboratory evaluations as specified in Appendix 1.
- Bleeding events (if not previously reported).
- Transfusions (if not previously reported).
- Disposition post-study CRRT Treatment Period.

If a patient discontinues from the study prematurely, every attempt should be made to perform all of the End of Treatment procedures and evaluations. Upon exiting the study, the patient will be treated per standard-of-care, which may or may not include continued CRRT.

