7.6 End of Study Procedures

After completion of study CRRT during the Treatment Period (up to 120 hours of study CRRT) AE/SAEs will be followed for a period of 30 days. All patients who complete up to 120 hours of study CRRT and the 30-day AE/SAE follow up period will successfully complete the study. Related AEs and SAEs will be followed post-study until resolution or stable.

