5.6 Safety Measures

- 1. Serum bicarbonate and pH will be measured at baseline and every 6 hours during the 120 hours Evaluation period and at 120 hours or end of the Evaluation period.
- 2. Blood total calcium concentrations will be measured at baseline, 1 hour and every 6 hours during the 120 hours evaluation period and at 120 hours or end of the Evaluation period from the initiation of CRRT.
- 3. Serum electrolytes (sodium, potassium, chloride, phosphate and, magnesium) will be measured at baseline and every 6 hours during the 120 hours evaluation period and at 120 hours or end of the evaluation period.
- 4. As indicators of citrate accumulation (along with pH), the total calcium/ iCa²⁺ ratio (both measurements in mmol/L) will be measured at baseline, 1 hour and every 6 hours during the 120 hours evaluation period and at 120 hours or end of evaluation period, anion gap and base excess will be measured at baseline and every 6 hours during the 120 hours evaluation period and at 120 hours or end of evaluation period.
- 5. The number, location and duration of bleeding events during the 120 hours Evaluation period will be collected. If a blood transfusion is needed during the 120 hours Evaluation period, the number and type of transfusions along with the number of units infused will be collected.
- 6. Change from baseline to final measurement in laboratory and vital signs measurements will be collected.
- 7. The incidence of adverse events (AEs) and serious adverse events (SAEs) from the time the patient signs the informed consent form (ICF) until the end of the study will be collected.

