14.1 Adverse Events (AEs)

The outcome/resolution of all AEs and SAEs will be determined by the Investigator and documented on the AE case report form (CRF)/SAE report form.

An overview of the number of subjects with at least one AE, at least one SAE, at least one study product-related AE, at least one study product-related SAE, and withdrawn due to SAE will be summarized (frequency and percentage of subjects).

An overview of the number of AEs, SAEs, study product-related AEs, and study product-related SAEs along with rates of events per subject treatment days will be tabulated.

The number of subjects with at least one AE (Serious and Non-Serious) will be summarized by MedDRA System Organ Class and MedDRA Preferred Term (frequency and percentage of subjects). The number of AEs (Serious and Non-Serious) and the rates of AEs per subject treatment days will be summarized by MedDRA System Organ Class and MedDRA Preferred Term. In addition, the number of subjects with at least one AE (Serious and Non-Serious) will be summarized by MedDRA System Organ Class, MedDRA Preferred Term and Severity (mild, moderate, severe) (frequency and percentage of subjects).

The number of subjects with at least one study-product related AE (Serious and Non-Serious) will be summarized by MedDRA System Organ Class and MedDRA Preferred Term (frequency and percentage of subjects). The number of study-product related AEs (Serious and Non-Serious) and the rates of study-product related AEs per subject treatment days will be summarized by MedDRA System Organ Class and MedDRA Preferred Term. In addition, the number of subjects with at least one study-product related AE (Serious and Non-Serious) will be summarized by MedDRA System Organ Class, MedDRA Preferred Term and Severity (mild, moderate, severe) (frequency and percentage of subjects).

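### SAP 14.1 counts adverse events over one window, from first study treatment to 30 days after a treatment of at most 120 hours, so the AE and SAE tables can blur an on-treatment difference between arms

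*SAP*

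**What the plan says.** **Length of treatment and follow-up.** Protocol 3.4: "Individual patients will participate in the study for up to 35 days with a study treatment period of up to 120 hours". Protocol 7.6 adds that after study CRRT "AE/SAEs will be followed for a period of 30 days", and Protocol 6.10 sets AE collection from consent to that same point. SAP 5.6 carries this over: AEs and SAEs from consent "until the end of the study will be collected".

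**The AE tables.** SAP 14.1: "The number of subjects with at least one AE (Serious and Non-Serious) will be summarized by MedDRA System Organ Class and MedDRA Preferred Term". The overview, severity and product-related tables follow the same pattern, and a patient with several events is shown once, at the worst severity. The only division by time is that events between consent and first study treatment are listed apart. Neither list of tables in the SAP names an on-treatment or treatment-emergent AE table. Protocol 8.6 item 7 gives no window either.

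**Care after study CRRT.** Protocol 7.5: "the patient will be treated per standard-of-care, which may or may not include continued CRRT". Under Protocol 7.1, sites must already be "users of citrate as an anticoagulant for CRRT circuits".

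**Other safety outputs.** The bleeding and transfusion tables are titled as covering the 120 hours. The calcium, acid-base and electrolyte summaries (SAP 13.3 and 14.3) are by time point during study CRRT.

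**The concern.** The arms differ by design only during study CRRT. After that both groups receive local care in or after the ICU, where many of the same AE terms are common whatever the earlier treatment. A patient with an event in week three counts in the arm's incidence exactly as one with an event on day two, and a patient with both counts once. The severity tables share the problem: a mild event on treatment followed by a severe one of the same term later appears as severe.

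At stake is how readable the by-arm safety comparison is. Someone looking for harm from the study solution would compare AE and SAE incidence by term, and that comparison mixes a short randomised period with a much longer one in which treatment is neither randomised nor specified. The point concerns patient counts and percentages. The denominator of the event rates is a separate matter.

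**Working it through.** **Reproducing the plan's own figure.** 120 h / 24 = 5 days; 5 + 30 = 35 days, as Protocol 3.4 states. Randomised treatment is 5/35 = 14% of the window and follow-up 30/35 = 86%. The treated share is smaller when study CRRT ends early.

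**Formula.** Let p be the risk of a given term during study CRRT and q the risk of a first occurrence afterwards. Incidence over the whole window is

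P = p + (1 − p)q.

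If q is the same in both arms, the difference is P₁ − P₀ = (p₁ − p₀)(1 − q). The ratio P₁/P₀ moves toward 1 as q rises.

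**Inputs.** The documents give no AE rates. The on-treatment risks (20% Prismocitrate, 5% Control) and the range of q are assumptions.

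| q (both arms) | Prismocitrate | Control | Difference (points) | Ratio |
|---|---|---|---|---|
| 0 (on-treatment only) | 20% | 5% | 15 | 4.0 |
| 2% | 0.20 + 0.80 × 0.02 = 21.6% | 0.05 + 0.95 × 0.02 = 6.9% | 14.7 | 3.1 |
| 5% | 0.20 + 0.80 × 0.05 = 24.0% | 0.05 + 0.95 × 0.05 = 9.75% | 14.25 | 2.5 |
| 20% | 0.20 + 0.80 × 0.20 = 36% | 0.05 + 0.95 × 0.20 = 24% | 12 | 1.5 |
| 40% | 0.20 + 0.80 × 0.40 = 52% | 0.05 + 0.95 × 0.40 = 43% | 9 | 1.2 |

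For a term that is rare after treatment, the difference barely moves and the ratio stays well above 1. For a common term, both fall markedly.

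**Unequal later risk.** Assume 30% against 10% on treatment (difference 20 points, ratio 3.0).
- Excess persists in the citrate arm (q = 30% against 20%): 0.30 + 0.70 × 0.30 = 51% against 0.10 + 0.90 × 0.20 = 28%. The difference widens to 23 points, although the ratio falls to 1.82.
- Later risk higher in Control (q = 30% against 40%): 51% against 0.10 + 0.90 × 0.40 = 46%. The difference falls to 5 points.

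The direction therefore depends on what happens after study CRRT, which the single-window table cannot show.

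**The case against.** **The main known harms already have treatment-period comparisons.** This stands. Systemic ionised calcium is modelled and shown against its threshold by time point (SAP 13.3). Bicarbonate, pH, total calcium, the calcium ratio, anion gap and base excess are handled likewise (SAP 14.3), and bleeding and transfusions are limited to the 120 hours. For calcium and acid-base these are likely to be more sensitive than AE terms, because Protocol 6.10 makes a laboratory abnormality an AE only if it needs intervention, causes discontinuation or exceeds local limits. A reader might infer that a real citrate harm would be reported as no difference. The documents do not support that.

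**No test of AE incidence is planned.** This also stands. The AE tables are frequencies and percentages, so a loss-of-power figure would describe a test that nobody intends to run.

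**Citrate in Control patients afterwards is not stated.** A reader might infer from Protocol 7.1 and 7.5 that Control patients will receive it. Those sections establish only that sites can use citrate and that CRRT may continue. The point does not need it: ordinary background events over 30 days are enough.

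**The related-AE tables and the listings help.** In part. Causality assessment considers timing (Protocol 6.10.1), so late events would tend to drop out. But causality is judged in an open-label trial, a missing assessment counts as related (SAP 14.1), and these tables have no onset window either. Listings carry start dates but give no incidence by arm.

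**Conclusion.** The point holds as a limited weakness in the safety reporting. The AE and SAE tables combine at most 5 days of randomised treatment with 30 days of non-randomised care, and nothing in the SAP separates the two. It matters mainly for clinical AEs and SAEs without a treatment-period laboratory or bleeding output, such as infection, hypersensitivity reactions or cardiopulmonary arrest, all on the anticipated list in Protocol 6.10.6.

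The size cannot be fixed from the documents. It runs from negligible on the difference scale when later risk is about 2%, to a ratio of 1.2 in place of 4.0 when it is 40%. Those figures rest on assumed on-treatment risks and on equal later risk in both arms. Dilution of the absolute difference is likely for common background terms but is not certain.

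**What to change.** In SAP 14.1, define an onset-period flag and produce the overview, SOC/PT, severity and related-AE tables, with the matching SAE tables, as follows:

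1. Onset from first study CRRT to the end of study CRRT plus a short margin stated in advance. This is the main by-arm comparison.
2. Later onset, to day 30 after study treatment.
3. The full-window table, kept as a further display.

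The data are already collected: AE start date and timing (Protocol 6.11) and the date and time study CRRT stopped (Protocol 7.4.1). If the recorded timing does not give a clock time, the flag works to the day and the margin should be stated in days. The rule should be fixed before by-arm data are reviewed.

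The cost is SAP wording, one derived variable and repeat runs of existing tables. The downsides are more tables and a margin that is a convention. Flagging follow-up events by standard-of-care CRRT should not be part of this change, because Protocol 7.4 to 7.6 list no post-study CRRT or anticoagulant data for collection.

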14.2 Bleeding Events and Transfusions

The location of bleeding events and the type of transfusions will be summarized using frequencies and percentages. The number of subjects with bleeding events, the number of bleeding events, the duration of bleeding events, the number of subjects requiring transfusions and the number of transfusions will be summarized presenting frequencies and percentages for categorized data observed, and summarizing the original data using the number of values n, mean, standard deviation, median, minimum and maximum. The estimated blood loss and the units transfused will be summarized using the same statistics. Bleeding events and transfusions resulting from complications related to blood loss will be listed by patient.

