3. INVESTIGATIONAL PLAN

3.1 Overall Study Design and Plan

This study is a multi-center, prospective, non-blinded, one to one randomized study. A total of 160 adult patients, 80 in each study arm, will be enrolled at up to 15 investigational sites in the United States (US) and Canada. Patients meeting all of the inclusion criteria and none of the exclusion criteria of this protocol, and deemed treatable by either CRRT with Prismocitrate 18 solution or CRRT with no systemic anticoagulation, are eligible for enrollment in the study. If a patient is already receiving standard-of-care CRRT, they must be randomized within 24 hours of initiation of their standard-of-care CRRT. All patients will be treated with predilution CVVHDF as the study CRRT modality. Patients enrolled in the study will receive either Prismocitrate 18 anticoagulation or no systemic anticoagulation during their study CRRT, and extracorporeal circuit life will be monitored for up to 120 hours of study CRRT (Treatment Period). During the Treatment Period, the adequacy of anticoagulation in the Prismocitrate 18 patients will be assessed by monitoring extracorporeal circuit pressures and by assessment of systemic and post-filter blood iCa concentrations. Patients will be monitored for acid-base parameters and serum electrolytes at baseline prior to any CRRT), initiation (after randomization but before the initiation of study CRRT) and at pre-determined intervals during treatment. Information on bleeding events (number, location, duration) and the number and type of blood transfusions along with the number

of units infused will also be collected. During the Treatment Period, the patient will be monitored at baseline and as detailed in Section 7.

See Appendix 1, Blood Sampling Schedule and Appendix 2, Schedule of Events Table.

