5.2 Treatment Administered

All patients in this study will be treated with the Prismaflex System Control Unit with Version 7.xx Software and the disposable Prismaflex M150 Set. The patients will be followed post-randomization for up to 120 hours from the initiation of study CRRT. This 120 hour post-randomization period will be referred to as the Treatment Period. At the time of randomization, if a patient is currently receiving CRRT, the standard-of-care CRRT extracorporeal circuit will be replaced with a new Prismaflex M150 Set. During the Treatment Period, patients will be treated up to 120 hours of study CRRT with either Prismocitrate 18 or no systemic anticoagulation. "Baseline" during the Treatment Period is defined as prior to any CRRT therapy, "Initiation" is defined as after randomization but before the initiation of study CRRT. Initiation may occur at the same time point as baseline, should enrollment and randomization occur prior to any CRRT therapy. Following data points will be collected during study CRRT for the duration of the Treatment Period:

- Extracorporeal circuit pressures will be measured and recorded by the Prismaflex System device in real time. The end of the extracorporeal circuit life will be defined by the occurrence of one or both of the following Prismaflex System alarms/conditions, if the alarms cannot be mitigated. At this point study CRRT will be terminated and the extracorporeal circuit replaced, because mitigation of the following alarms is not possible:
 - "Warning: Filter Clotted", and/or
 - "Advisory TMP Too High"

Note: The nurse at the clinical site will document the alarm and rationale to stop treatment on the eCRF. In addition, the Prismaflex logging information from the data cards (one card per patient) will be collected on an ongoing basis and anonymized data will be sent to Baxter for technical analysis. An Independent Adjudicator will make the final determination of the alarm cause (see Section 9.9 Primary Endpoint Adjudication).

- Serum bicarbonate and pH will be measured at baseline, initiation of study CRRT, at 6 hour intervals and at 120 hours or end of the Treatment Period (see Appendix 1).

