6.8 Safety Assessments

Safety endpoints include:

1. Serum bicarbonate and pH will be measured at baseline, initiation and every 6 hours during the 120 hour Treatment Period and at 120 hours or end of the Treatment Period.

- 2. Blood total calcium concentrations will be measured at baseline, initiation, 1 hour and every 6 hours during the 120 hour Treatment Period and at 120 hours or end of the Treatment Period from the initiation of study CRRT.
- 3. Serum electrolytes (sodium, potassium, chloride, phosphate, magnesium, and anion gap) and base excess will be measured at baseline, initiation and every 6 hours during the 120 hour Treatment Period and at 120 hours or end of Treatment Period
- 4. As indicators of citrate accumulation (along with pH), the total calcium/iCa ratio (both measurements in mmol/L) will be measured at baseline, initiation, 1 hour and every 6 hours during the 120 hour Treatment Period and at 120 hours or end of Treatment Period, anion gap and base excess will be measured at baseline, initiation and every 6 hours during the 120 hour Treatment Period and at 120 hours or end of Treatment Period.
- 5. The number, location and duration of bleeding events during the 120 hour Treatment Period will be collected. If a blood transfusion is needed during the 120 hour Treatment Period, the number and type of transfusions along with the number of units infused will be collected.
- 6. Change from baseline to final measurement in laboratory and vital signs measurements will be collected.
- 7. The incidence of adverse events and serious adverse events from the time the patient signs the informed consent form (ICF) until the end of the study will be collected.

6.9 Analysis of Training on Administration of Prismocitrate 18

The end users who need to be assessed prior to use of Prismocitrate 18 in the clinical trial setting (as delegated by an investigator) will be comprised of physicians, nurses, and other clinicians who may be part of prescribing, initiating, or modifying treatment during the 120 hour Treatment Period. The assessment materials,

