8.6 Safety Endpoints

Analysis of safety endpoints will be carried out on the FA Set based on the actual treatment groups for the following parameters:

- 1. A MMRM analysis will be used to evaluate differences between treatment groups in the change from baseline in serum bicarbonate and pH that are collected every 6 hours from the initiation of study CRRT during the 120 hour Treatment Period and at 120 hours or end of the Treatment Period. Frequencies and percentages will be provided for pH < 7.2 by time point and treatment group (thresholds indicative of metabolic acidosis).
- 2. A MMRM analysis will be used to evaluate differences between treatment groups in the change from baseline in blood total calcium concentrations that are assessed at 1 hour and every 6 hours from the initiation of study CRRT during the 120 hour Treatment Period and at 120 hours or end of the Treatment Period.
- 3. A MMRM analysis will be used to evaluate differences between treatment groups in the change from baseline in serum electrolytes (sodium, potassium, chloride, phosphate, and magnesium) that are collected every 6 hours from the initiation of study CRRT during the 120 hour Treatment Period and at 120 hours or end of the Treatment Period.

- 4. A descriptive summary of the total calcium/systemic iCa ratio as assessed at baseline, at initiation of study CRRT, 1 hour and every 6 hours from the initiation of study CRRT during the 120 hour Treatment Period and at 120 hours or end of the Treatment Period will be provided by treatment group. Frequencies and percentages will be provided for total calcium/systemic iCa ratio > 2.1 by time point and treatment group (threshold suggestive of citrate accumulation). Frequencies and percentages will be provided for anion gap > 11 mmol/L by time point and treatment group (threshold indicative of metabolic disturbance) as well as for base excess < -5 mmol/L.
- 5. A descriptive summary of the number, location, and duration of bleeding events along with the estimated blood loss during the 120 hour Treatment period will be provided by treatment group. The number and type of blood transfusion along with the number of units infused will also be summarized.
- 6. An analysis of covariance (ANCOVA) model will be used to evaluate differences between treatment groups in the change from baseline to final measurement in laboratory and vital signs measurements.

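### Bleeding and transfusion summaries in SAP 14.2 have no observation-time denominator, so they mix bleeding rate with time at risk if time on study CRRT differs between arms

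*SAP*

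**What the plan says.** **Analysis.** SAP section 14.2 plans frequencies, percentages and the usual descriptive statistics: "the number of bleeding events, the duration of bleeding events, the number of subjects requiring transfusions and the number of transfusions will be summarized". Estimated blood loss and units transfused are handled in the same way. Tables 14.3.1.1 to 14.3.1.4 are titled for the 120-hour evaluation period. Protocol section 8.6 calls for "A descriptive summary of the number, location, and duration of bleeding events along with the estimated blood loss during the 120 hour Treatment period", by treatment group. Neither document plans a test or a rate for these data.

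**Collection.** Protocol section 6.8: "The number, location and duration of bleeding events during the 120 hour Treatment Period will be collected". In the Schedule of Events (Protocol Appendix 2; SAP Table 1), the bleeding and transfusion rows are ticked only in the column for the study CRRT treatment period. Protocol section 7.5 places the closing procedures "after completion of study CRRT during the Treatment Period (up to 120 hours of study CRRT"), and its list includes "Bleeding events (if not previously reported"), with a matching item for transfusions.

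**Length of the window.** Protocol section 3.1: "extracorporeal circuit life will be monitored for up to 120 hours of study CRRT (Treatment Period"). Protocol section 5.2: "This 120 hour post-randomization period will be referred to as the Treatment Period".

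**Adverse events.** For adverse events and serious adverse events, SAP section 14.1 says that "rates of events per subject treatment days will be tabulated".

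**The concern.** Time on study CRRT varies between patients. Eligibility asks only for an expected 72 hours on CRRT after randomization, and the cap is 120 hours. A patient who stops at 72 hours has been observed for 72/120 = 60% of the time named in the table titles. Time on study CRRT is also a post-randomization outcome, which tolerance of citrate or the clinical course could change differently in the two arms.

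If mean time differs, an arm can show more bleeding events, or more patients with a bleed, because it was watched for longer. In the same way, an arm whose patients stop early can look safer than it is. Bleeding and transfusion are named in the study's secondary objectives, and readers will take the side-by-side table as the bleeding comparison whether or not a test accompanies it. SAP section 14.1 deals with this for adverse events; section 14.2 does not.

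**Working it through.** The documents give no bleeding rate and no expected CRRT duration by arm, so there is no planned figure to reproduce. What follows is an illustration. All exposures and rates are assumptions; only the 80 patients per arm comes from the documents.

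**Set-up.** Bleeding follows a Poisson process with the same rate λ per patient-day in both arms, so there is no true difference. All patients within an arm share one exposure of T hours.

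- Expected events = 80 × λ × T/24
- Proportion of subjects with at least one event = 1 − exp(−λT/24)
- Count ratio = T(Prismocitrate 18)/T(Control)

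**Worked case, λ = 0.10, 90 against 60 hours.**

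- Events: 80 × 0.10 × 90/24 = 30.0, and 80 × 0.10 × 60/24 = 20.0. The ratio is 1.50.
- Subjects with at least one event: 1 − exp(−0.375) = 31.3%, and 1 − exp(−0.25) = 22.1%.
- Patient-days: 80 × 90/24 = 300, and 80 × 60/24 = 200.
- Rates: 30/300 = 0.10, and 20/200 = 0.10. The rate ratio is 1.00.

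**Range, λ = 0.10.**

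| Hours, Prismocitrate 18 / Control | Events | Count ratio | Subjects with at least one event | Rate ratio |
|---|---|---|---|---|
| 90 / 90 | 30.0 / 30.0 | 1.00 | 31.3% / 31.3% | 1.00 |
| 90 / 80 | 30.0 / 26.7 | 1.125 | 31.3% / 28.3% | 1.00 |
| 90 / 60 | 30.0 / 20.0 | 1.50 | 31.3% / 22.1% | 1.00 |
| 100 / 50 | 33.3 / 16.7 | 2.00 | 34.1% / 18.8% | 1.00 |
| 70 / 90 | 23.3 / 30.0 | 0.78 | 25.3% / 31.3% | 1.00 |

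At 90 against 60 hours, the spurious difference in the percentage of subjects is 5.3 points if λ = 0.05 and 13.4 points if λ = 0.20.

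**Direction.** With unequal rates, the counts tie when the true rate ratio equals T(Control)/T(Prismocitrate 18). For 90 against 60 hours that is 60/90 = 0.67. A longer-observed arm with a lower bleeding rate need not show more events.

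**Which window applies.** Protocol sections 3.1 and 7.5 describe a period that ends with study CRRT. One sentence in section 5.2 describes a fixed 120-hour period after randomization, but the same section also speaks of treatment for up to 120 hours of study CRRT. No scheduled bleeding or transfusion collection covers the interval between an early CRRT stop and hour 120. Separately, footnote e of the Schedule of Events says that an alarm that cannot be mitigated ends the patient's treatment period, whereas Protocol sections 5.2 and 6.7.1 have the set replaced. These passages contradict each other.

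**The case against.** A reader might infer that the bias is built in: that whichever arm stays on CRRT longer must show more bleeding, and that the plan tests the arms on raw counts. The documents do not support that.

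- **Unequal exposure is not established.** Both arms have the same 120-hour cap and the same entry criterion. Shorter circuit life in Control does not by itself shorten observation if the set is replaced and CRRT continues. With equal exposure the distortion is zero. This stands, and so the point is conditional.
- **The summaries are descriptive.** No test is planned, and subject percentages are given as well as counts. This also stands, although percentages are affected too. In the worked case their ratio is about 1.4, against 1.50 for counts.
- **On the fixed-window reading of Protocol section 5.2, the windows would be nearly equal** apart from death and withdrawal. This is fair as far as the definition goes, but the scheduled collection does not carry that reading through for these data.
- **Exposure adjustment exists elsewhere.** Bleeding is on the list of anticipated adverse effects (Protocol section 6.10.6), so bleeding reported as an adverse event gets a treatment-day rate under SAP section 14.1. SAP section 11 also summarises CRRT duration. This is a partial safeguard only. Adverse events are collected to 30 days after treatment, which does not match a treatment-day denominator, and transfusions and units are not covered.
- **A rate has its own assumption.** It averages over time and assumes a roughly constant hazard. If bleeding clusters early, the rate counts against the arm that stops sooner. This stands, and is the reason to keep the counts.

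**Conclusion.** The point holds in conditional form. SAP section 14.2 and Tables 14.3.1.1 to 14.3.1.4 report bleeding and transfusion for a nominal 120 hours with no denominator, while scheduled collection appears to end with study CRRT. If mean time on study CRRT differs between arms, the tables mix bleeding rate with time at risk. With equal rates, the count ratio is simply the exposure ratio: 1.125 to 2.00 when the Prismocitrate 18 arm is assumed to be observed longer, 0.78 in the assumed reverse case, and 1.00 when exposures are equal. These figures rest on assumed exposures, a constant rate and a common exposure within each arm, so they say nothing about the size or direction to expect in this trial.

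This is a reporting gap in a named secondary safety objective, worth closing because the remedy is nearly free. It does not show that the bleeding results will be biased.

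**What to change.** 1. In SAP section 14.2, add bleeding-event and transfusion rates per patient-day of study CRRT observation, by arm. Define the denominator (first start to final end of study CRRT) and say whether interruptions count.
2. In Tables 14.3.1.1 to 14.3.1.4, add total and mean observed time by arm. Keep the existing counts and percentages beside the rates. A rate ratio with a patient-clustered interval is optional.
3. Reconcile the Treatment Period definitions (Protocol sections 3.1 and 7.5 against the fixed-period sentence in section 5.2), and footnote e of the Schedule of Events in both documents against Protocol sections 5.2 and 6.7.1, so that the observation window is unambiguous. If a fixed window is meant, the bleeding and transfusion collection must cover it and the denominator must follow it.

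The cost is a few table lines and a wording change. Start and end times of study CRRT are already recorded under Protocol section 7.4.1, so items 1 and 2 need no new data.
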